5 ANALYSIS VARIABLES

5.1 Primary Efficacy Endpoint:

- Pediatric EoE Symptom Score (PEESS, version 2). The PEES total score change from pre-treatment to post-treatment is the primary efficacy endpoint. The Parent Report for Children and Teens PEES will be used as the primary.

The PEES total score comprises of two types: frequency and severity. A total of 11 frequency questions and 9 severity questions are there respectively. The raw scores of 0 to 4 will be converted to 0 to 100 by multiplying each score by 25. The total metric score is calculated as the mean of non-missing items from the 20 total possible. If more than 50% (10 items) are missing for a particular patient on a visit, the score will not be calculated, rather set as missing.

There are four domains: Dysphagia, GERD, Nausea/vomiting, and Pain. Domain specific scores are calculated similarly.

Dysphagia:

How often does your child have trouble swallowing?

How bad is your child's trouble swallowing?

How often does your child feel like food gets stuck in his/her throat or chest?

How bad is it when your child gets food stuck in his/her throat or chest?

How often does your child need to drink a lot to help swallow food?

How bad is it when your child needs to drink a lot to help swallow food?

How often does your child eat less than others?

How often does your child need more time to eat than others?

GERD:

How often does your child have heartburn (burning in the chest, mouth, or throat)?

How bad is your child's heartburn (burning in the chest, mouth, or throat)?

How often does your child have food come back up in his/her throat when eating?

How bad is it when food comes back up in your child's throat?

Nausea/vomiting:

How often does your child vomit (throw up)?

How bad is your child's vomiting (throwing up)?

How often does your child feel nauseous (feel like throwing up but does not)?

How bad is your child's nausea (feeling like throwing up, but does not)?

Pain:

How often does your child have chest pain, ache, or hurt?

How bad is your child's chest pain, ache, or hurt?

How often does your child have stomach aches or belly aches?

How bad are your child's stomach aches or belly aches?

5.2 Secondary Efficacy Endpoints:

- Patient Related Outcome (PRO) metrics pre- and post-treatment
 - PedsQL EoE Module
 - Generic Health Related Quality of Life measures
 - PROMIS General Health Questionnaire and PedsQL
 - Individual domain PEES scores
- Histology and endoscopy measures
 - Percent of participants who achieve histologic remission (<15 peak eosinophils/HPF) post therapy assessed after the end of the 3 months
 - Division of patients into complete (all peak eosinophils ≤1/HPF) or partial (the worse of 3 scores is from 2 to 14) remission, and non-remission (at least one > 14/HPF)
 - Histology Scoring system
 - Endoscopic scoring system (EREFS)
- Biomarkers pre- and post-treatment
 - Assessment of Eosinophil Diagnostic Panel EoE Score
- Clinical parameters and biomarkers to predict responsiveness to diet and SGC therapy

- Correlation of clinical characteristics to response to therapy
- Assessment of predictive value of skin prick and patch allergy skin testing
- Correlation between presence of positive milk component allergy testing to response to 1FED
- Predictive biomarker-analysis of EoE transcriptome from EDP analysis on baseline biopsies in correlation to response to treatment.

5.2.1.1 Secondary End-Point Analysis: Biomarkers

In this sub-aim, we hypothesize that molecular biomarkers will change (improve) with each treatment phase, at least in part. Furthermore, we hypothesize that biomarkers may reveal (a) novel insight into therapeutic resistance and/or relapse; (b) reveal patient sub-groups not identified by histology; and (c) ultimately prove to be readily usable biomarkers in clinical settings and possess personalized medicine value. We will focus on molecular profiling of esophageal genes with the Eosinophil Diagnostic Panel (EDP), a set of 94 mRNA transcripts that have been established to differentiate EoE from controls (e.g. GERD and normal individuals), and to identify exposure and transcriptional signaling to SGCs²⁸. Essentially, the associated EDP algorithm renders the raw Ct values of each embedded gene after real-time PCR in a way that the upregulated genes and down-regulated genes are summed up individually. A quantitative “EoE score” is derived from the ΔCt (normalized to GAPDH) summation to reflect disease severity and for statistical analysis. Utilizing different gene sets, EDP is also able to predict steroid exposure and remission status based on the same algorithm²⁸. In this case, the EoE score will be calculated at baseline endoscopy and in the post-treatment biopsies to assess change with treatment.

The change in “EoE score” will be analyzed between responders and non-responders based on histology assessment (<15 eosinophils/HPF) at the end of Phase I via an ANOVA model, after proper transformation of the score, e.g. logarithmic if needed. If normality assumption is seriously violated, a non-parametric method of Wilcoxon test will be applied.

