7.2 Screening (Weeks -12 To -1)

Participants will be screened as above in Table 1. The screening visit should occur at a maximum of twelve weeks prior to the enrollment visit. The research staff member will perform the informed consent process after obtaining informed consent, the following study procedures should be performed and documented up to twelve

weeks prior to the enrollment (Week 0) visit:

- Assess eligibility (inclusion and exclusion criteria)
- Collect medical, surgical and diet history
- Vitals (height, weight, blood pressure, heart rate, respiratory rate, temperature)
- Demographics (age, gender, race)
- Physical exam performed by a study clinician or qualified staff member
- Obtain CBC with differential
- Obtain up to 4 biopsies from the distal and proximal esophagus for research purposes (taken during standard of care EGD)
 - One of these esophageal biopsies will be used for EDP
- Research lab samples (blood or saliva) for future genetic testing may be collected at this visit
- Assessment of concomitant medications and therapies
- Provide food diary
- Pregnancy Test (urine)

Esophageal biopsies for research may be taken during a participant's standard of care EGD (SOC EGD). If the participant has had a SOC EGD and biopsies performed at a participating site or at an outside institution prior to the screening visit (and consent), the results of the EGD may be used to determine eligibility if it falls within the twelve-week window prior to enrollment. In these cases, research biopsies and EREFS evaluation will not be required at baseline. EGDs performed at an outside institution may be used as baseline if the corresponding pathology report and slides are available and the eosinophil counts meet the inclusion criterion of ≥ 15 eosinophils/hpf. In cases where the local pathologist has concerns regarding the eosinophil count, slides may be sent to the CRPC for rapid review in order to verify eligibility. These participants will have all other screening procedures completed at the in-office, screening visit.

CBC results will be obtained from a participant's standard of care lab. The amount of blood drawn (clinical plus research) will adhere to institutional policy limits.

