7.5 End Of Treatment Phase I Or Early Withdrawal (Week 12)

For participants who have completed the 12 week Phase I or have withdrawn early from the study, the following procedures will occur:

- Measure vitals (blood pressure, heart rate, respiratory rate, temperature), height and weight

PCORI Diet Study

- Physical exam performed by study clinician or qualified staff member
- Administer patient and parent-reported outcome questionnaires
- Assess AEs
- Obtain up to 4 biopsies from the distal and proximal esophagus for research purposes (taken during standard of care EGD)Research lab samples:
 - Esophageal biopsy for EDP
 - Serum (~2 tsp, or 10 mL) for serum IgE/CRD/IgG4
 - Blood or saliva for future genetic testing may be collected at this visit
- Obtain CBC with differential (SOC)
- Assess participant compliance with diet and concomitant medications
- Pregnancy Test (urine)

If a participant withdraws from the study before completing 12 weeks of dietary therapy, the end of treatment/early withdrawal visit, should be conducted within one week of the participant's stopping dietary therapy. Participants should stay on their dietary therapy until results of biopsies are communicated to them. Those participants who have resolution of their inflammation on endoscopy will complete the study at this time while those with continued active inflammation will move on to the next phase, which consists of either 4FED (for Phase I 1FED non-responders) or swallowed fluticasone therapy at 880 mcg twice a day while back on an unrestricted diet (for Phase I 4FED non-responders).

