1.2 Secondary Objectives

- To extend Phase I of this study with a prospective non-blinded trial that determines the rate of remission after treatment with 4FED (in participants failing 1FED in Phase I) or SGC (in participants failing 4FED in Phase I) (Phase II).
- To evaluate the effect of each therapy on histological remission (defined as a post therapy eosinophil count of <15 eosinophils/HPF) and by a variety of changes in eosinophils, including (a) pre- and post-therapy peak eosinophil counts; (b) partial remission (2-14 peak eosinophils/hpf); and (c) complete histological remission (≤ 1 peak eosinophils/hpf).
- To evaluate the effect of each therapy by utilizing the histology scoring system (HSS) created to express the severity and extent of other abnormalities in the gastrointestinal (GI) tract that often accompany eosinophilic inflammation.
- To determine the impact of each therapeutic intervention on biomarkers using the EoE Diagnostic Panel (EDP).
- To evaluate the clinical and psychosocial effect of each therapy using the Peds Quality of Life Inventory Eosinophilic Esophagitis Module (PedsQL EoE) to assess EoE symptoms and problems/feelings related to eating.
- To determine if any clinical parameters predict response to therapeutic intervention.
- To determine if any biomarkers including component-resolved diagnostics (CRD) [serum IgE component testing] predict response to therapeutic intervention.
- To determine if skin testing, in the form of prick and patch testing, predicts response to therapeutic intervention.
- Also to assess relationship between primary PEES score changes and histological scores (HSS).

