- (2) Remission rates will be compared between the two treatment groups using the generalized linear mixed effects model with the logit link (for binary outcome) that accounts for the clustering within sites. Important covariates will be analyzed in this model including gender, race, PPI use, atopy, age, and anthropomorphic features. Treatment group comparisons for secondary endpoints will be performed using the generalized linear mixed effects model using the link that is appropriate for the endpoint (i.e. logit for binary, log for Poisson count, identity for continuous). These models will account for the clustering within sites and will include the same covariates as for the primary analysis.
- (3) The remission rate for non-responders who proceed to Phase II will be summarized separately depending on the treatment patients received during Phase I and Phase II. The 95% confidence interval for the rates will also be provided.

6.2 Statistical Analyses: Aim 2

To evaluate the ability of biomarkers and phenotypic characteristics to predict response to therapeutic intervention, multivariable logistic regression analysis may be conducted with histological evaluation of remission/no remission as the dependent variable and biomarker levels as the independent variables. Multicollinearity of the independent variables will be assessed. The area under the receiver operating characteristic curve (AUROC) will be estimated along with 95% confidence interval. This analysis will be conducted based on the remission status at the end of Phase I. It may also be repeated at the end of Phase II by including those patients who also responded to SGC.

Additionally, a correlation analysis between PEES scores and biomarkers will be performed. Spearman's correlation coefficient and its confidence intervals will be computed to further assess predictive utility for the biomarkers of interest.

Missing data will be handled in the following manner. For the primary efficacy measure of PEES, each patient is expected to complete the questionnaire; even if the patient terminates participation early (dropout) for any reason. The total PEES score is the average of 20 item scores, as long as there are at least 10 item response non-missing, as described previously. No imputation of missing total PEES will be performed. The early dropout reasons will be recorded, and rates will be assessed between treatment groups for potential patterns.

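### The EoE-score analysis written in SAP 5.2.1.1 tests association with histologic response; change on each treatment, and any change in Phase II, is left unestimated

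*SAP*

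**What the plan says.** SAP 1.2 (Secondary Objectives) sets the aim: "To determine the impact of each therapeutic intervention on biomarkers using the EoE Diagnostic Panel (EDP". Protocol 5.2 has the same objective.

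SAP 5.2.1.1 turns it into a hypothesis, "we hypothesize that molecular biomarkers will change (improve) with each treatment phase, at least in part", and describes the measurement: "the EoE score will be calculated at baseline endoscopy and in the post-treatment biopsies to assess change with treatment". It adds further hypotheses on therapeutic resistance, on patient subgroups that histology does not identify, and on clinical usability.

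The analysis in the same section takes the change in that score, which "will be analyzed between responders and non-responders based on histology assessment (<15 eosinophils/HPF) at the end of Phase I via an ANOVA model", with a Wilcoxon test if normality fails badly. Neither diet arm nor Phase II is mentioned.

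Other relevant text:
- SAP 5.2 lists "Assessment of Eosinophil Diagnostic Panel EoE Score" as a secondary endpoint.
- SAP 6.1 step (2) says "Treatment group comparisons for secondary endpoints will be performed using the generalized linear mixed effects model", with an identity link for continuous outcomes. The covariates are those of the primary analysis, and baseline EoE score is not named among them.
- SAP 6.1 step (3), on Phase II, covers remission rates only.
- Protocol Table 1 and sections 7.5 and 7.8 schedule an EDP biopsy at Weeks 12 and 25.
- Protocol 7.2 allows a qualifying EGD done before consent: "In these cases, research biopsies and EREFS evaluation will not be required at baseline".

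**The concern.** The hypothesis concerns change over time on each treatment. The test written for it compares groups of children defined by a post-treatment result. Its null is that the change in EoE score does not differ between histologic responders and non-responders. The objective needs a different quantity, namely the mean change on a given treatment or the difference in mean change between the diets.

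The two can come apart in either direction. If all children improve by a similar amount, whatever their histology, the responder comparison sees nothing. If responders improve and non-responders worsen so that the mean is unchanged, it can be clearly significant.

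At stake is how the EDP result will be read. The one p-value dedicated to the EoE score sits under a hypothesis about improvement with treatment that it does not test. The Week 25 EDP data on 4FED after 1FED, and on SGC after 4FED, have no planned analysis of change in the score.

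**Working it through.** The documents give no sample size, power or effect size for this analysis, so there is no stated figure to reproduce. The check is a comparison of questions and analyses, followed by an illustration.

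**Question against analysis**

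| Question | Where it is answered |
|---|---|
| Does the score change on 1FED, on 4FED (Phase I)? | Nowhere |
| Does it change on 4FED or SGC in Phase II? | Nowhere |
| Does change differ between 1FED and 4FED? | SAP 6.1 step (2), general clause |
| Does change differ by histologic response at end of Phase I? | SAP 5.2.1.1 ANOVA |
| Do baseline transcripts separate responders from non-responders? | SAP 5.2.2.1 |
| Do biomarkers predict remission, or correlate with PEES scores? | SAP 6.2 |

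The between-diet contrast cannot stand in for the first two rows. Two diets that improve the score equally give a contrast of zero.

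**Illustration**

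Inputs from the documents: about 50 participants (SAP 4.1), randomised 1:1, taken as 25 per diet; response 45% and 65% (Protocol 12.1); alpha 0.05 (SAP 6.1). Assumptions: two-sided t-tests, SD of change = 1, every child has a paired score, and the effect sizes below.

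Expected responders: 25 × 0.45 + 25 × 0.65 = 27.5. Expected non-responders: 50 − 27.5 = 22.5.

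- A: every child improves by 1 SD.
- B: mean change is zero in each diet, but responders do 1 SD better than non-responders. In 1FED, 0.45 × 0.55 + 0.55 × (−0.45) = 0. In 4FED, 0.65 × 0.35 + 0.35 × (−0.65) = 0.
- C: only responders improve, by 1 SD. Mean change is 0.45 on 1FED and 0.65 on 4FED.
- D: no change in anyone.

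Share of 5,000 simulated trials with p < 0.05:

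| Scenario | Responder vs non-responder (SAP 5.2.1.1) | Within 1FED | Within 4FED | 4FED vs 1FED |
|---|---|---|---|---|
| A | 5% | 99.7% | 99.8% | 5% |
| B | 90% | 5% | 5% | 5% |
| C | 93% | 48% | 81% | 11% |
| D | 5% | 5% | 4% | 5% |

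A and B show that the written test neither detects a shared improvement nor requires a net one. C shows that it is the most powerful of the four tests when only histologic responders improve.

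**Precision available**

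At the protocol's response rates, Phase II would hold about 25 × (1 − 0.45) = 13.75, say 14, on 4FED and 25 × (1 − 0.65) = 8.75, say 9, on SGC, before dropout and missing biopsies. The 95% CI half-width is t × SD / √n:
- n = 25: 2.064 / 5 = 0.41 SD
- n = 14: 2.160 / 3.742 = 0.58 SD
- n = 9: 2.306 / 3 = 0.77 SD

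**The case against.** The strongest reply is that the plan already holds the only randomised evidence on this endpoint. The EoE score is a listed secondary endpoint, and SAP 6.1 step (2) compares the diets on secondary endpoints. That stands. A reader might infer that the SAP has no treatment comparison for EDP, and that would be wrong.

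It can also be said that the responder comparison suits the section's other hypotheses, on resistance and clinical usability. That stands too, and the analysis should be kept.

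Other stronger readings are tempting, and the documents do not support them:
- *The test merely compares two readouts of one endoscopy.* The post-treatment EDP biopsy and the response classification come from the same Week 12 EGD, but the change score also uses the baseline value. Association of molecular change with histologic response is the exact description.
- *The diets are pooled in the ANOVA.* The SAP is silent on diet, so pooling is an inference.
- *The test has a large false-positive rate.* With zero mean change and 55% remission, it rejects in 38%, 84% and 99.7% of simulated trials if score change correlates 0.3, 0.5 or 0.7 with follow-up eosinophils. These figures are power against the test's own null, which is false at any non-zero correlation. At 0.5 to 0.7 they also need non-responders to worsen by 0.44 to 0.62 SD. The correlation is not in the documents.
- *A significant ANOVA will be reported as improvement.* The SAP does not say so. The risk lies in the placement and lack of a label.

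Within-treatment tests are not clean either. Children enter with at least 15 eosinophils/hpf, so some pre-post change may be regression to the mean. In a no-effect model of visit-to-visit fluctuation, the within-diet test rejected about 5 to 11% of the time.

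**Conclusion.** The concern holds in limited form. The analysis written in SAP 5.2.1.1 answers a legitimate question, but not the one in the section's leading hypothesis or in the secondary objective. Two things are missing: an estimate of EoE-score change within each treatment, and any analysis of EoE-score change in Phase II.

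That conclusion rests on the text alone. The rejection rates (5% in A, 90% in B, 93% in C) only illustrate direction. They depend on assumed effects, SD and complete pairing, and complete pairing is optimistic because baseline research biopsies may be absent.

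The importance is minor to moderate. This is one of several secondary endpoints in a trial reduced to about 50 children, and the primary analysis is unaffected.

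**What to change.** In SAP 5.2.1.1:

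1. Report mean change in EoE score with 95% CI for Phase I 1FED, Phase I 4FED, Phase II 4FED and Phase II SGC. Give the paired N for each, and state which biopsy is the reference for the Phase II change. Describe these as uncontrolled pre-post changes that may include regression to the mean.
2. Name the SAP 6.1 step (2) 1FED–4FED contrast as the randomised treatment comparison for this endpoint, and add baseline EoE score as a covariate.
3. Keep the responder/non-responder ANOVA. Label it as association of EDP change with histologic response, and state that it is not evidence that a therapy changes the biomarker. Say whether diet is a factor in it.

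The cost is a paragraph of SAP text and a few analyses on samples already scheduled. The price is a more modest EDP claim and wide Phase II intervals, roughly ±0.6 to ±0.8 SD at the protocol's response rates. Baseline adjustment also drops children without a baseline EDP biopsy unless the SAP says how they are handled.

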5.2.2 AIM 2: Clinical Parameters & Biomarkers That Predict Therapeutic Response

5.2.2.1 Predictive Biomarker-Analysis Of EoE Transcriptome

In this sub-aim, we aim to identify biomarkers that may predict responsiveness to any or all of the treatment

interventions associated with this trial. As such, in this sub-aim, we will perform the EDP analysis on baseline biopsies, focused on identifying transcript levels that differentiate patients that respond to each of the interventions.

Baseline esophageal gene expression was compared between responders and non-responder patients by statistically screening two cohorts. A list of genes with $p < 0.05$ (or $FDR < 0.05$), fold change > 2.0 will be identified.

5.3 End of Therapy (EOT) And Follow-Up

The primary efficacy endpoint (e.g. PEES v2 scoring) will be determined at the end of Phase I & II (weeks 12 & 25) at which time all participants will undergo EGD with biopsy. Histologic scoring of biopsy samples obtained during the end of Phase I endoscopy, will be used to determine the treatment pathway to be followed. Participants who achieve histologic remission at the end of Phase I will have completed the study and will resume follow-up care with their primary GI and/or Allergy physician(s). Those whose disease remains active in terms of histologic disease activity (eosinophil count ≥ 15 per HPF) will go on to Phase II (twelve week treatment with 4FED for Phase I 1FED non-responders **OR** SGC for Phase I 4FED non-responders).

6 STATISTICAL METHODS

6.1 Statistical Analyses: Aim 1

Demographic and patient characteristics will be summarized for the two treatment groups using mean \pm standard deviation or median [interquartile range] for continuous variables and frequency and percentages for categorical variables. Treatment comparisons will be performed using the two-sample t-test or Wilcoxon Rank sum test for continuous variables and the Fisher's Exact test for categorical variables. All tests will be conducted at $\alpha=0.05$, including the primary and secondary analyses.

There was going to be two sets of analysis populations in terms of efficacy assessment, the intent-to-treat and per protocol. However, since the total enrollment has been reduced to about 50, all patients randomized to Phase I of the study who have at least one clinical observation post randomization will be considered in intent-to-treat set. Only this set of population will be included in the statistical analyses. Originally, we plan to define patients who are at least 80% compliant to dietary assignment during Phase I, and who do not have any major protocol violations as in per protocol set. Now all analyses will be based on intent-to-treat population. Patients who do drop out of the trial before the end of Phase I will have their PEES done at the time of dropout. The primary endpoint is overall PEES score change from pre-treatment to the end of Phase I. If normality assumption is approximately valid, a linear mixed effect model will be applied to the primary efficacy variable,

account for site random effect, and other potentially important covariates, e.g. gender, race, and PPI use etc. Because of non-normal nature of the scores in previous research, a Wilcoxon rank sum test may be applied to compare between two treatment groups when normality is violated.

As a secondary endpoint analysis, remission rates (as defined by the percentage of participants achieving histologic remission (eosinophils less than 15/HPF) at the end of Phase I will be analyzed in the following 3 steps.

- (1) Remission rates will be computed along with their 95% CIs for each diet group separately;
- (2) Remission rates will be compared between the two treatment groups using the generalized linear mixed effects model with the logit link (for binary outcome) that accounts for the clustering within sites. Important covariates will be analyzed in this model including gender, race, PPI use, atopy, age, and anthropomorphic features. Treatment group comparisons for secondary endpoints will be performed using the generalized linear mixed effects model using the link that is appropriate for the endpoint (i.e. logit for binary, log for Poisson count, identity for continuous). These models will account for the clustering within sites and will include the same covariates as for the primary analysis.
- (3) The remission rate for non-responders who proceed to Phase II will be summarized separately depending on the treatment patients received during Phase I and Phase II. The 95% confidence interval for the rates will also be provided.

6.2 Statistical Analyses: Aim 2

To evaluate the ability of biomarkers and phenotypic characteristics to predict response to therapeutic intervention, multivariable logistic regression analysis may be conducted with histological evaluation of remission/no remission as the dependent variable and biomarker levels as the independent variables. Multicollinearity of the independent variables will be assessed. The area under the receiver operating characteristic curve (AUROC) will be estimated along with 95% confidence interval. This analysis will be conducted based on the remission status at the end of Phase I. It may also be repeated at the end of Phase II by including those patients who also responded to SGC.

Additionally, a correlation analysis between PEES scores and biomarkers will be performed. Spearman's correlation coefficient and its confidence intervals will be computed to further assess predictive utility for the biomarkers of interest.

Missing data will be handled in the following manner. For the primary efficacy measure of PEES, each patient is expected to complete the questionnaire; even if the patient terminates participation early (dropout) for any reason. The total PEES score is the average of 20 item scores, as long as there are at least 10 item response non-missing, as described previously. No imputation of missing total PEES will be performed. The early dropout reasons will be recorded, and rates will be assessed between treatment groups for potential patterns.

For all other secondary efficacy and demographic variables, missing data will not be imputed. However, if a participant's biomarker panel is partially missing, multiple imputation may be applied for missing markers in predictive modeling analyses.

Heterogeneity of treatment effect is referred to as the variability in the direction and magnitude of individual or subgroup treatment effects that are non-random. Descriptive heterogeneity of treatment effect analyses will first be carried out for subgroups by gender, by study site, and by age of subject. These analyses are included in the analysis plan above for primary and secondary efficacy analyses, where proper estimates of treatment effect will be extracted. Because of the small sample size in this study, any hypothesis testing of treatment heterogeneity is considered exploratory. P-values generated from multiple comparisons are not adjusted. The goal is to identify possible heterogeneity among subgroups for further confirmation. The interaction of demographic and baseline characteristics with treatment group effects may be tested in the generalized linear mixed effects models to assess heterogeneity.
